7.1.4 Serious Adverse Events

An SAE is defined as any event that:

- Results in death (including suicide)
- Is life-threatening
- Results in inpatient hospitalization or prolongation of existing inpatient hospitalization

- Planned admissions for respite care are not to be considered an SAE (the medical monitor should be contacted for confirmation regarding whether or not an admission for respite care should be considered planned or unplanned). Unplanned admissions for respite care will constitute an SAE unless it is as a result of caregiver needs that are independent of the subject's condition.
- An admission or prolongation of existing hospitalization because the subject does not want to be discharged, or because the caregiver is unable or unwilling to care for the subject, is not to be considered an SAE.
- Admissions to a hospital that were planned or anticipated before the start of the study for an unrelated pre-existing medical condition are not to be considered an SAE.
- Results in persistent or significant disability or incapacity
- Is a congenital anomaly or birth defect
- Other medically significant events that require immediate medical or surgical intervention.

Medical and scientific judgment should be exercised in deciding whether an event is serious and whether expedited reporting is appropriate in other situations, such as important medical events that may not be immediately life-threatening or result in death or hospitalization but may jeopardize the subject or may require intervention to prevent one of the outcomes listed in the definitions above.

All SAEs must be reported on the eCRF. An assessment should be made by the investigator of whether the event is study-drug related, *i.e.*, is 'causally' related to the study drug.

7.1.5 *Pregnancy*

Pregnancy is to be considered an immediately reportable event. This includes pregnancy of a female subject or a female sexual partner of a male subject.

Subjects who become pregnant during the clinical study should discontinue study drug immediately and contact the investigator.

Subjects should be instructed to notify the investigator of a pregnancy either during the treatment period of the study or within 3 months after the last dose of study drug.

Whenever possible, a pregnancy should be followed to term, any premature terminations reported, and the status of the mother and child should be reported to the Sponsor after delivery.

Although the pregnancy is not considered to be an AE or SAE, any pregnancy complications should be recorded as AEs or SAEs (if applicable). Any pregnancy should be followed through delivery for the observation of any SAE. Therefore, regardless of whether or not a pregnancy is actually considered an SAE, a pregnancy form should be completed for all pregnancies.

Pregnancies should initially be reported in the Pregnancy Notification Form, Part I and sent by e-mail to the following address:

[contact].

When the outcome of the pregnancy is known, site personnel will complete the Pregnancy Notification Form, Part II and e-mail it to the following address:

[contact].

All data related to pregnancy, pregnancy outcome, and SAE associated with pregnancy will be recorded in a safety database maintained by personnel responsible for pharmacovigilance at Worldwide Clinical Trials.

7.1.6 Reporting Requirements and Timeframes

The requirements for reporting SAEs and pregnancies are described below. A Safety Management Plan will be implemented to further describe and document the process for safety reporting.

7.1.6.1 Investigator Reporting of SAEs and Pregnancy to Sponsor

If any of the adverse events are SAEs as defined by this protocol (see Section 7.1.4) or a pregnancy (see Section 7.1.5), special procedures will be followed. All such events will be reported to the Sponsor designee, Worldwide Clinical Trials, immediately (and not exceeding 24 hours following knowledge of the event) and followed by follow-up reports as soon as possible, whether or not the events are deemed study drug-related.

Serious Adverse Events must be reported by entering the SAE information in the AE/SAE section of the Electronic Data Capture (EDC) system. The information provided in the EDC system should be as complete as possible, but must contain the following minimum fields:

- Subject number
- Brief description of the SAE (diagnosis or signs/symptoms)
- Serious criteria
- Causality assessment
- Assessment of the intensity of the event

WCT Drug Safety will receive notification of the initial SAE *via* an e-mail alert generated from the EDC system. In the event of any temporary disruption of the EDC system, an alternative SAE reporting mechanism will be available to site personnel; in this instance, a paper SAE Report Form will be available. Site personnel will complete the paper SAE report form, scan and e-mail it within 24 hours to the following address:

[contact]

Site personnel must complete the AE/SAE section with the SAE information as soon as the EDC system becomes available. Serious adverse events that are ongoing should be followed until resolved or stabilized to a level acceptable to the investigator.

The investigator is obliged to provide additional information as requested by the medical monitor. In general, this will include a description of the event in sufficient detail to

allow for a complete medical assessment of the case and independent determination of possible causality. In the case of a subject death, a summary of available autopsy findings, if performed, must be submitted as soon as possible to the contract research organization. However, any supporting information provided should not reveal a subject's identity beyond the agreed study identifier. The investigator should ensure that information reported is accurate and consistent.

Information not available at the time of the initial report (*e.g.*, an end date for the AE, laboratory values received after the report, or hospital discharge summary) must be documented on a follow-up form. All follow-up information must be reported in the same timelines as initial information.

Any SAEs considered related to the study drug and discovered by the investigator at any interval after the study must also be reported to the Sponsor within 24 hours following knowledge of the event.

7.1.6.2 *Sponsor Reporting of SUSARs to Regulatory Authorities*

Suspected, unexpected serious adverse reactions (SUSARs) are adverse events that are believed to be related to an investigational medicinal product and are both unexpected (*i.e.*, the nature or severity is not expected from the information provided in the Investigator's Brochure) and serious. As stated in the EU 'CT-3' Communication from the Commission (2011/C 172/01) and the US Code of Federal Regulations (21 CFR 312.32), for there to be a reasonable possibility of a causal relationship between the event and study drug there must be facts (evidence) or arguments to suggest a causal relationship. Final assessment of expectedness for purposes of regulatory reporting is the responsibility of the Sponsor.

It is the responsibility of the Sponsor to determine whether a reported SAE fits the classification of a SUSAR and to notify the investigator of the decision as soon as possible. Requirements for SUSAR reporting are described below. All SUSAR reporting will adhere to European Directives 2001/20/EC, 21 CFR 312.32 of the U.S. Code of Federal Regulations, Health Canada Food and Drug Regulation C.05.014, and other regions as applicable.

7.1.6.2.1 Unblinding Treatment Allocation

As this is an open-label study, treatment allocation in this study is by default unblinded for all SUSAR reporting to the pertinent regulatory authorities. The onset of a possible SUSAR relative to the prior treatment history is an important aspect of the assessments. Therefore, should treatment assignment in the previous double-blind study of participation (*i.e.*, Studies TRx-237-005, TRx-237-007, TRx-237-008, and TRx-237-015) not yet be unblinded, the treatment assignment for a given subject will be made available for assessment of the SUSAR and will be included in the reporting of the event to a regulatory authority (as of implementation of Amendment 3.0).

When an event may be a SUSAR, the blind should be broken only for that specific subject. The blind should be maintained for individuals responsible for the ongoing conduct of the study (*e.g.*, management, monitors and investigators) and those

responsible for data analysis and interpretation of results at the conclusion of the study (e.g., biometrics personnel).

Unblinded information should only be accessible to those who need to be involved in the safety reporting to pertinent regulatory authorities, independent ethics committees/independent review boards (IECs/IRBs) and DSMBs, or individuals performing ongoing safety evaluations during the study.

7.1.6.2.2 Fatal or Life-threatening SUSARs

It is the responsibility of the Sponsor to report fatal or life-threatening SUSARs to the pertinent regulatory authorities as soon as possible, but no later than 7 calendar days (or earlier if locally mandated). These will be reported to the DSMB in parallel.

7.1.6.2.3 Other SUSARs

It is the responsibility of the Sponsor to report other SUSARs to the pertinent regulatory authorities as soon as possible, but no later than 15 calendar days (or earlier if locally mandated). These will be reported to the DSMB in parallel.

7.1.6.3 Reporting to IECs/IRBs

The IEC/IRB will be notified of any SUSARs according to local regulations and within the designated timeframe.

The investigator (or prospectively agreed to designee) is required to notify the IEC/IRB of any fatal SUSAR as soon as possible but no later than 7 calendar days after he/she first became aware of the reaction (or earlier if locally mandated).

The investigator (or prospectively agreed to designee) is required to notify the IEC/IRB of any other SUSAR as soon as possible but no later than 15 calendar days after he/she first became aware of the reaction (or earlier if locally mandated).

7.2 Urgent Safety Measures

The Sponsor and investigator may take appropriate urgent safety measures in order to protect the subjects of the clinical study against any immediate hazard to their health or safety.

The Sponsor and the Medical Monitor or designated deputy will be notified of any urgent safety measures taken by the investigator or qualified designee and advised of their responsibility to notify the licensing authority. The investigator or qualified designee will notify the IEC/IRB.

If these measures are taken, the Sponsor or investigator shall immediately give written notice to the pertinent regulatory authorities consistent with the regional/national requirements and IEC/IRB of the measures taken and the circumstances giving rise to those measures. In any event, the written notice shall be no later than 7 days from the date the measures are taken.

7.3 Clinical Laboratory Tests

Scheduled blood samples for hematology and chemistry panels will be obtained at each visit during the study, including Baseline (if not available within the prior 42 days), after 2 weeks, and approximately every 13 weeks (relative to Baseline) thereafter (or upon early termination). Laboratory testing will be repeated at the 4-week post-treatment follow-up visit if applicable.

A trained and authorized person will collect blood samples from the subject by venipuncture from a suitable vein.

Kits with supplies for the collection of blood samples will be provided to each study site before the study initiation visit. The kits will be labeled to identify the clinical study, and will include specimen labels, pre-printed laboratory requisition forms, all supplies needed for specimen collection and shipping, instructions for collection and preparation of specimens, and pre-printed forms to expedite shipment.

A protocol-specific laboratory manual will be provided to each study site. The laboratory manual will include contact details, lists of the contents of collection kits, shipment schedule of collection kits, and detailed guidelines and recommendations for completing laboratory requisition and for specimen collection, preparation, storage, and transportation.

A central laboratory will process all scheduled laboratory blood samples unless otherwise noted. Data will be transferred electronically for inclusion in the database. Investigators are to enter the results of any testing performed at local laboratories (and the corresponding normal ranges) into the eCRF.

7.3.1 Serum Chemistry

The blood volume for each chemistry panel will be approximately 3.5 mL. Blood samples collected for serum chemistry panels are to be destroyed approximately 1 week after testing has been completed. The chemistry panel will include the following analytes:

Sodium	Gamma-glutamyl transpeptidase (GGT)
Potassium	Alanine transaminase (ALT)
Calcium	Aspartate transaminase (AST)
Albumin	Glucose (random, not fasted)
Total protein	Creatinine ²
Urea nitrogen, urea ¹	Phosphorus
Total and direct (conjugated) bilirubin (indirect bilirubin calculated as the difference)	Uric acid
Alkaline phosphatase	Chloride
Lactate dehydrogenase (LDH)	Creatine kinase (CK)

¹ The analytical method measures urea in serum. In the Covance CLS database, the test is named either Urea Nitrogen or Urea, depending on whether the results are expressed in conventional or SI units, respectively. Urea Nitrogen is reported in mg/dL while Urea is reported in mmol/L per SI unit convention.

² Creatinine clearance is to be estimated by the central laboratory using the Cockcroft-Gault equation.

7.3.2 *Hematology*

The blood volume for each hematology panel will be approximately 2.0 mL. Blood samples collected for hematology panels are to be destroyed approximately 3 days after testing has been completed. The hematology panel will include the following analytes:

Hematocrit	White blood cells (WBC)
Hemoglobin	and absolute and percent differential
Mean corpuscular hemoglobin (MCH)	(neutrophils, lymphocytes, monocytes, eosinophils, basophils); any abnormal cells
Mean corpuscular hemoglobin concentration (MCHC)	will be noted
Red blood cells (RBC) and any immature forms	Platelet count
RBC morphology	Mean cell volume (MCV)
Reticulocyte count and percent	

If the investigator is concerned on the basis of significant hematological abnormalities that Heinz bodies may be present, a blood sample may be sent to the local laboratory for assessment and screening of Heinz bodies. The percent of erythrocytes with Heinz bodies should be reported based on a suitably prepared slide; blood samples should be as fresh as possible at the time of slide preparation. If Heinz bodies are present, study medication must be stopped (see Section 6.2.3.1) and another blood sample should be obtained within 1 week. Hematological indices should continue to be monitored until this resolves.

7.3.3 *Other Laboratory Tests*

A serum pregnancy test for qualitative testing for the beta subunit of human chorionic gonadotropin (β -hCG) will be obtained for all women of childbearing potential at Baseline (if the Baseline visit does not coincide with the final double-blind study visit) and each subsequent study visit (or upon early termination). In the event of a borderline result, testing will be repeated and if the result is still borderline, quantitative testing for β -hCG will be performed.

7.3.4 *Review of Laboratory Results*

Laboratory results from each study visit will be assessed in a timely manner. The investigator or an authorized physician sub-investigator must interpret the laboratory findings and confirm their review.

The clinical significance of all laboratory values which are outside the laboratory normal reference range should be noted and commented upon by the investigator.

Abnormal values which are considered by the investigator to be clinically significant, taking the age of the subject into account, should be documented as an AE, unless

accounted for by a pre-existing medical condition detailed in the subject's medical history. The diagnosis associated with a clinically significant laboratory abnormality generally should be recorded as the underlying abnormality or diagnosis (*e.g.*, renal insufficiency) if there is sufficient overall information to permit a diagnosis to be made by the investigator. Otherwise, the observed deviation in the laboratory result should be recorded (*e.g.*, elevated creatinine).

The investigator must review and assess laboratory results for clinically significant abnormalities. If any of these suggest hemolytic anemia, treatment interruption should be considered (see Section 6.2.3.1).

Additional tests and other evaluations required to establish the significance or etiology of an abnormal result or to monitor the course of an AE may be obtained from the central laboratory. If a local laboratory needs to be used in some circumstances, the data and corresponding normal ranges will be recorded in the eCRF, entered directly from a laboratory slip. When clinically indicated, the medical monitor should be informed in such circumstances. In particular, if a clinically significant abnormal result is observed that is not resolved by the following visit, repeated tests should be performed until resolution of the abnormality.

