6.2.3.1 Hemolytic Anemia

When there are clinical symptoms and/or laboratory signs of hemolytic anemia, dosing should be discontinued. Clinical symptoms are described in Section 7.1.3.1 and laboratory signs are described in Section 7.3.2. Follow-up laboratory monitoring is also

⁵ Administrative reasons (or other reasons not related to safety) are not to be considered safety reasons warranting treatment discontinuation.

described in Section 7.3.2. The medical monitor should be contacted to discuss whether or not resumption of dosing is indicated or for any other questions.

6.2.3.2 *Serotonin Syndrome*

Subjects are to be monitored at each visit by a medically qualified person for signs and symptoms indicative of potential serotonin toxicity, especially when initiating LMTM in this study or any medication with serotonergic potential. At each post-Baseline visit, subjects are to be evaluated by targeted physical and neurological examination and measurement of temperature, respiratory rate, blood pressure, and pulse (see Section 7.1.3.2 for guidance on assessment). Should serotonin syndrome (toxicity) be suspected clinically, treatment should be immediately discontinued. The event should be reported as an AESI and the medical monitor should be contacted for further guidance on subject management.

6.2.3.3 *Other Safety Reasons Requiring Dose Adjustment*

Treatment should be discontinued if the following treatment-emergent change occurs on ECG (based on the means of the three recordings) without other explanatory cause:

- QTcF interval > 500 msec: repeat ECGs should be obtained, in triplicate, within 2 weeks; if confirmed by the mean of the repeat ECGs, study drug should be discontinued pending further evaluation.

Other clinically significant changes in the ECG should be discussed with the medical monitor.

If renal concerns arise and the calculated creatinine clearance is < 30 mL/min, study drug should be discontinued.

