7.1.3.1 Hemolytic Anemia

The subject should be evaluated at each visit for possible clinical symptoms associated with hemolytic anemia, in conjunction with review of hematology results. Should hemolytic anemia be suspected, follow-up testing should be performed as described in Section 7.3.2. The medical monitor should be contacted to discuss whether or not resumption of dosing is indicated or for any other questions.

The signs and symptoms of anemia include:

- Cyanosis, headache, anxiety, exercise intolerance, fatigue, confusion, dizziness, tachypnea, palpitation, dysrhythmia, seizures, and coma

Signs of possible hemolytic anemia include:

- Decrease by 20% from Baseline in RBC count and/or hemoglobin
- Abnormal RBCs in peripheral blood smear
- Elevation of reticulocyte count to above laboratory normal range
- Increase in LDH or indirect bilirubin, or low haptoglobin

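### Protocol 7.3.4 makes stopping drug optional when laboratory results suggest hemolytic anemia, while 6.2.3.1, which it cites, directs a stop; 6.2.3.1 also omits 7.1.3.1 from its laboratory-sign reference

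*Protocol*

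**What the plan says.** Section 7.3.4, on the investigator's review of laboratory results, says of clinically significant abnormalities: "If any of these suggest hemolytic anemia, treatment interruption should be considered". The sentence ends with a reference to Section 6.2.3.1.

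Section 6.2.3.1 says: "When there are clinical symptoms and/or laboratory signs of hemolytic anemia, dosing should be discontinued". It continues: "Clinical symptoms are described in Section 7.1.3.1 and laboratory signs are described in Section 7.3.2". It then provides for a possible restart: "The medical monitor should be contacted to discuss whether or not resumption of dosing is indicated".

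Section 7.1.3.1 lists the signs of possible hemolytic anemia. They include "Decrease by 20% from Baseline in RBC count and/or hemoglobin" and "Increase in LDH or indirect bilirubin, or low haptoglobin". It also says: "Should hemolytic anemia be suspected, follow-up testing should be performed as described in Section 7.3.2".

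Section 7.3.2 gives the hematology analytes and an instruction on Heinz bodies: if present, drug must be stopped and a further sample taken within 1 week. It gives no other criterion for hemolytic anemia.

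**The concern.** Section 7.3.4 is where an investigator looks when a laboratory report arrives. It makes interruption a matter for consideration, yet the section it cites directs a stop, and does so on laboratory signs alone because of the and/or. Following the reference exposes the difference without settling it.

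Hemolytic anemia is one of only two adverse events of special interest, and Section 4.7.8 acknowledges a risk of anemia with the drug. With about 170 sites, the same results could lead one site to stop and call the medical monitor, and another to consider interruption and carry on dosing. What is at stake is consistent protection of subjects.

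**Working it through.** The plan states no figure to reproduce. The check is a comparison of text, followed by the visit spacing.

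**1. Action and trigger, side by side (current Version 3.0 text)**

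| Section | Trigger | Action |
|---|---|---|
| 6.2.3.1 | symptoms and/or laboratory signs | stop directed; medical monitor contacted on resuming |
| 7.3.4 | laboratory abnormalities that suggest it | interruption to be considered |
| 7.1.3.1 | hemolytic anemia suspected | follow-up testing; medical monitor contacted on resuming |
| 7.3.2 | Heinz bodies present | stop mandatory |

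Because 6.2.3.1 allows resumption, its stop can work as an interruption. The conflict is therefore not interruption against permanent discontinuation. It is a directed action against a discretionary one.

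**2. Does any section grade the response?** The triggers differ in wording (results that suggest the condition, against signs of it), but 7.1.3.1 calls its own list signs of *possible* hemolytic anemia, so they overlap. Sections 6.2.3 and 7.1.3 mention interruption as well as discontinuation, but give no rule for choosing. Section 5.3 speaks of clinically evident hemolytic anemia and refers back to 6.2.3.1. Section 7.1.3.1 mentions resumption, which presupposes a stop that it does not itself state. None of these reconciles the pair.

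**3. Where the laboratory signs are.** Section 7.1.3.1 has 4 entries: red cell count and/or hemoglobin, smear, reticulocytes, and LDH/indirect bilirubin/haptoglobin. Section 7.3.2 lists analytes for 3 of the 4. For the fourth, LDH and bilirubin are in 7.3.1 and haptoglobin is in neither panel. Section 7.3.2 sets a criterion for none of the 4; its only one is Heinz bodies. The reference in 6.2.3.1 is thus incomplete, though not empty. Section 2 shows why the fuller list matters: the Phase 3 hemolytic anemia case described there was Heinz body negative and recovered with treatment interruption. One case supports no rate.

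**4. Visit spacing.** Target days in Figure 4-1: 15, 92, 183, 274, 365. Windows: ±3 days at Day 15, ±14 at the others.

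- Visit 2 to 3: 92 − 15 = 77 days; widest (92 + 14) − (15 − 3) = 106 − 12 = 94 days.
- Visit 3 to 4: 183 − 92 = 91 days; widest (183 + 14) − (92 − 14) = 197 − 78 = 119 days.
- Visits 4 to 5 and 5 to 6: 274 − 183 = 91 and 365 − 274 = 91 days; widest 288 − 169 = 119 and 379 − 260 = 119 days.
- Baseline to Visit 2 is shorter: 15 − 1 = 14 days.

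Section 7.3.4 requires repeat tests only when a clinically significant abnormality has not resolved by the next visit, so this spacing is the relevant interval for a site relying on 7.3.4 alone.

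**The case against.** The strongest reply is that 7.3.4 is a review section that sends the reader to 6.2.3.1 for the action, so a site relying on 7.3.4 alone must ignore the reference in the same sentence. That makes divergence less likely. It does not remove it, because a reader who follows the reference finds a different instruction and nothing to say which governs.

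The safeguards are also substantial. Section 7.1.3.1 calls for symptom evaluation with hematology review at every visit and for testing on suspicion. Section 7.3.4 requires physician review and permits additional tests at any time. Section 7.1.3 has the medical monitor informed by the laboratory or the site, so notice need not depend on the site. The Week 6 call falls inside the first-year gap between Visits 2 and 3, and unscheduled visits are available. All of this stands.

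The cross-reference point is minor: 6.2.3.1 already sends the reader to 7.1.3.1 for symptoms, where the laboratory signs follow directly, and 6.2.3 points to 7.1.3 for monitoring.

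A reader might infer that subjects with hemolysis would be dosed for 77 to 119 days. The documents do not support that: these figures describe the visit schedule, and the safeguards act within it. A reader might also infer that 6.2.3.1 itself needs a new trigger, with an exemption for an isolated LDH rise. The documents supply no clinical ground for one, and it would loosen the stricter rule.

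**Conclusion.** The conflict is real: one pair of sections, directed against discretionary, with no reconciling text, and one incomplete reference of minor effect. It should be corrected, but it is a wording defect in site safety conduct and nothing larger. The documents give no count of affected subjects, so the practical effect cannot be sized beyond the visit spacing, and that overstates exposure wherever the safeguards work.

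No statistical result is affected. A reader might suspect that the adverse-event tables are compromised, but SAP Section 7.1 tabulates the dose action recorded for each event and no analysis depends on which stopping instruction a site followed.

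The conclusion assumes that results which suggest hemolytic anemia will often be the same results that 6.2.3.1 treats as laboratory signs. The heading of the list in 7.1.3.1 supports that overlap.

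**What to change.** Make two wording changes.

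- **Section 7.3.4:** replace the sentence with: *If, in the investigator's judgment, any of these suggest hemolytic anemia, dosing should be stopped, follow-up testing performed, and the medical monitor contacted on whether to resume (see Sections 6.2.3.1 and 7.1.3.1).*
- **Section 6.2.3.1:** change the laboratory-sign reference to *Sections 7.1.3.1 and 7.3.2*.

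Leave the trigger in 6.2.3.1 and the Heinz-body stop in 7.3.2 as they are, and add no LDH exemption. The protocol already pairs suspicion with a directed stop for the other event of special interest, in Section 6.2.3.2: "Should serotonin syndrome (toxicity) be suspected clinically, treatment should be immediately discontinued".

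The change settles the action. It leaves to the investigator whether results suggest hemolysis, so some variation remains. That is reasonable: of the 4 entries in 7.1.3.1, 1 states a size of change (20%), 1 refers to the normal range, and 2 give neither.

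No visit, test or analysis is added. If the amendment is substantial it needs prior ethics and regulatory approval (Section 11), so it is best bundled with the next one. Some subjects later found not to have hemolytic anemia will have a reversible interruption. Under 6.2.2 a single safety interruption of more than 30 days ends treatment, so follow-up testing and the decision on resuming must be prompt.
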